Short et al, 2006[26]	52.5-55 Gy in 20 fractions	2.63 Gy, 2.75 Gy	66.3 Gy 70.1 Gy	98.5 Gy 105.4 Gy
Yamazaki et al, 2006[9]	63 Gy in 28 fractions	2.25 Gy	77.2 Gy	110.3 Gy

STU122017-043, [name], FormA-ResearchProtocol, Mod_29, 02-07-22

Conventional	66 Gy in 33 fractions 70 Gy in 35 fractions	2 Gy	79.2 Gy 84 Gy	110 Gy 116.7 Gy
--------------	--	------	------------------	--------------------

Table 3. Biologically effective doses (BED) of prior hypofractionated radiation regimens used for early stage glottic larynx cancer, assuming an α/β of 10 for a rapidly growing tumor, an α/β of 6 for a slow-moderate growing tumor and an α/β of 3 for late toxicities of normal tissues.

Given that patients with a larger PTV and active smoking history were at greater risk for toxicity (albeit encompassing only 3 patients in total) **in our study**, we have therefore decided to treat this population with the Dutch regimen. In particular, patients with:

- PTV greater than or equal to 10 cc
- Smoking within 1 month of registration

will be treated with daily SBRT at a dose of 58.08 Gy in 16 fractions. Because patients with small tumors from the phase I portion of the trial had minimal toxicity with treatment, we propose to continue the dose of 42.5 Gy in 5 fractions for tumors less than 10 cc.

Radiation Therapy Delivery

There are a number of different techniques used to deliver highly-focal, inverse planned radiation therapy. The Erasmus group used a static-field IMRT approach.[23] Static-field IMRT is a commonly used approach where the beam angles are pre-chosen and then the radiation delivery is inversely planned by the planning system. The downside of static-field IMRT is that 7-9 beam treatment requires up to 30 minutes to complete.

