A third option for treating a focal larynx cancer is with the use of volumetric modulated arc therapy (VMAT), which is essentially an IMRT treatment delivered from nearly 360 degrees around the patient. This allows for many more beam angles than static field IMRT and it also allows for a much quicker treatment. One group recently compared 2-arc VMAT with a typical 8-field IMRT plan for early stage larynx cancer and reported that both target volume coverage and homogeneity were comparable between VMAT and IMRT, while VMAT was superior for carotid-artery sparing. Additionally, VMAT delivery time was significantly faster than with IMRT (3-5 minutes vs. 5-10 minutes).[29] Another study supports the substantially reduced treatment time with arc therapy vs. IMRT.[30] Because of the promising results with VMAT treatment delivery, either modality (i.e. CyberKnife or VMAT) is acceptable for treatment on this protocol.

Summary points

- 1. Local control rates using a highly focal radiation target appear to be as good as conventional radiation therapy (≥80%)
- 2. Highly focal radiation therapy targeting only the involved site of disease plus a small margin delivers an extremely low dose of radiation dose nearby structures based on both the Dutch Erasmus and the UT Southwestern Phase I studies.
- 3. A reduced dose to nearby structures might improve toxicities, such as esophagitis and stroke from carotid atherosclerosis and could reduce the decline in voice function from contralateral cord dose. However, long-term follow-up of voice quality of life following focal larynx radiation therapy is not yet available from the phase I portion of this trial.
- 4. Hypofractionated radiation therapy appears to be safe, although there were three cases of soft tissue necrosis in the phase I trial. Current smoking status and larger PTV volume (> 10cc) all had qualitatively higher rates of necrosis.
- 5. Based on the phase I study, we propose using a dose of 42.5 Gy in 5 fractions for low-risk tumors: tumors with a PTV < 10cc, no recent smoking, and disease limited to the vocal process. This provides both an adequate tumoricidal dose, and a limited dose to normal tissues. Remaining patients will be irradiated using the Dutch 16 fraction regimen.
- 6. Treatment with either Cyberknife or VMAT will be acceptable.

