2.2 Secondary Objectives

2.2.1 To determine patient-reported outcomes (PRO) following treatment with SBRT.

- 2.2.2 To describe the rates of grade 3-5 acute and late toxicities following treatment with SBRT.
- 2.2.3 To characterize patient utilities using EQ5D following treatment with SABR.
- 2.2.4 To determine the patterns-of-failure following SBRT. Specifically, 2-year cumulative risk of in-field, marginal, and out-of-field local failure, regional and distant failure, laryngectomy-free survival, disease-specific survival and overall survival following treatment with SBRT.

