4.0 TREATMENT PLAN

4.1 Treatment Dosage and Administration

Radiation will be delivered twice per week for 5 fractions (42.5 Gy cohort, low-risk) or daily for 16 fractions (58.08 Gy cohort, moderate-risk).

Low-risk is defined by:

- PTV less than 10 cc, AND
- No reported smoking within 1 month from registration

Moderate-risk is defined by:

- PTV greater than or equal to 10 cc, OR
- Smoking within 1 month from registration (no more than 1 pack per day)

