4.2 Toxicities and Dosing Delays/Dose Modifications

Any subject who receives treatment on this protocol will be evaluable for toxicity. Each patient will be assessed for the development of toxicity according to the Time and Events table in Section 5.4. Toxicity will be assessed according to the NCI Common Toxicity Criteria for Adverse Events (CTCAE), version 4.0.

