4.8 Subject Replacement

Subjects may be replaced in the study if they do not complete radiotherapy. Inadequate receipt of treatment may lead to a higher than expected recurrence rate, and therefore these patients may be replaced. Patient replacement must be verified through review of the case by the P.I.

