10.3 Data Analyses Plans

10.3.1 Primary endpoint: 2-year cumulative risk of local failure (i.e. anywhere in the larynx) following SBRT treatment of early glottic larynx cancer

This endpoint will be calculated using cumulative incidence statistics, with death as a competing risk.

10.3.2 Secondary endpoints:

Patient-reported outcomes: Difference in PRO voice quality measures between baseline and 1, 3, 6, 12, 18, 24, and 36 months following treatment:

10.3.2.1	VHI voice-quality score
10.3.2.2	EORTC QLQ-C30
	 Global health status
	 Physical functioning scale
	Role functioning scale
	Emotional functioning scale
	Cognitive functioning scale
	 Social functioning scale
10.3.2.3	EORTC HN35
	Speech
	 Social eating
	— • • • •

Social contact

These patient reported outcomes are single numeric scores that are collected at baseline, 1, 3, 6, 12, 18, 24 and 36 months from treatment. Patients with disease recurrence will be excluded. The changes in these outcomes from baseline to these timepoints will be analyzed using generalized estimated equations (GEE).

10.3.2.4 Rate of grade 3-5 acute (start of treatment through 90 days from the completion of treatment) and late (after 90 days from the completion of treatment) adverse events, according to NCI's CTCAE v4.0 toxicity criteria.

Only adverse events assessed to be definitely, probably, or possibly related to protocol treatment will be considered. The rates of all Grade 3-5 adverse events, and death during or within 30 days of discontinuation of protocol treatment will be characterized. Predictors of high-grade acute and late toxicity will be determined using multivariable logistic regression.

10.3.2.5Average patient utilities (derived from EQ-5D) at baseline, 3, 6,
12, 18, 24 and 36 months from the end of treatment

The average patient utilities (derived from EQ-5D) at baseline, 3, 6, 12, 18, 24 and 36 months from the end of treatment will be described. Changes in patient utility will be analyzed using generalized estimated equations (GEE). These models will be used to estimate the beta coefficient for dysphonia and grade 2-3 dysphagia, to produce an estimate of the utility decrement from this toxicity.

10.3.2.6 Cumulative risk of marginal and out-of-field local failure at 2 years from the start of treatment with death and prior in-field local failure as a competing risk

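### With 25 patients, too few grade 3-5 events are likely to support the multivariable logistic model that is meant to identify toxicity predictors, and its covariates are not named

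*Combined protocol and SAP*

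**What the plan says.** Section 10.3.2.4 restricts toxicity to events at least possibly related to treatment, characterises the grade 3-5 rates, and then adds: "Predictors of high-grade acute and late toxicity will be determined using multivariable logistic regression". It gives no covariates, number of terms, selection rule, minimum event count or sparse-data method. For recurrence, sections 10.3.2.6 and 10.3.2.7 ask only for univariable predictors.

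The matching objective in section 2.2 is more modest: "To describe the rates of grade 3-5 acute and late toxicities following treatment with SBRT". Section 10.2 sets the sample at 25 on local control alone. The toxicity denominator could be slightly larger, since section 4.2 says "Any subject who receives treatment on this protocol will be evaluable for toxicity" and section 4.8 says "Subjects may be replaced in the study if they do not complete radiotherapy".

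The rationale (section 1.4) suggests two candidate predictors without adopting them for the model. It says "patients with a larger PTV and active smoking history were at greater risk for toxicity (albeit encompassing only 3 patients in total", and its summary points add that "there were three cases of soft tissue necrosis in the phase I trial". Section 4.1 uses the same two variables to assign regimen. The low-risk, 5-fraction group needs a PTV below 10 cc and "No reported smoking within 1 month from registration". The moderate-risk, 16-fraction group is "PTV greater than or equal to 10 cc, OR" recent smoking.

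**The concern.** A logistic model learns from the patients who have an event. If only a handful of 25 do, a model with several terms may have no finite solution, because some combination of covariates separates events from non-events. Where a solution exists, its intervals may be too wide to use. Leaving the covariates open also allows them to be chosen after the data are seen.

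The risk is that an undefined or very unstable odds ratio is reported as a predictor of severe toxicity. The covariates that the rationale points to are also the ones that decide the regimen, so an apparent smoking or PTV effect could be a regimen effect, or the reverse.

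**Working it through.** The plan gives no event count, rate or power for this model, so there is no figure of its own to reproduce.

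**Expected events.** Patients with an event = 25 × rate. At 5% this is 25 × 0.05 = 1.25; at 10%, 2.5; at 20%, 5.0; at 30%, 7.5. The rates are assumptions. The 10% value matches the phase I necrosis count, 3/30, but that is one event type, pooled over dose levels, and only a proxy. With a binomial count at 10%, the chance of no event is 7% and of five or more 9.8%. Acute and late toxicity are separate outcomes, so neither can exceed the total.

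**When a finite fit exists.** With recent smoking (yes/no) and continuous PTV, ordinary maximum likelihood has a finite solution only if smokers and non-smokers each include both events and non-events, and PTV overlaps between events and non-events.

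**Hand check of the first condition.** Assume 8 recent smokers, 17 others and no true association. The chance that all k events fall in one group is [C(17,k) + C(8,k)] / C(25,k):
- k = 2: (136 + 28)/300 = 55%
- k = 3: (680 + 56)/2,300 = 32%
- k = 5: (6,188 + 56)/53,130 = 12%

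The overlap condition on PTV adds to these.

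**Simulation.** There were 18 settings: recent smokers 20, 30 or 40%; log-normal PTV with median 8, 9 or 10.6 cc and log-SD 0.3 or 0.5. There was no true association, the event count was fixed, n was 25, and 700 data sets were drawn per setting and count. All settings are assumptions. CI ratio means the upper limit divided by the lower limit of the Wald 95% interval for the smoking odds ratio, among finite fits.

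| Events | No finite fit, smoking + PTV: mean (range) | No finite fit, regimen added | Typical CI ratio |
|---|---|---|---|
| 2 | 60% (50-70) | about 100% | 460 |
| 3 | 39% (26-54) | 81% | 220 |
| 5 | 20% (8-34) | 48% | 120 |
| 8 | 9% (1-22) | 21% | 51 |

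A Wald interval is symmetric on the log scale, so the estimate must exceed the square root of the ratio before the interval excludes 1. That is about 15 at 3 events (√220) and about 7 at 8 events (√51).

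Averaged over a binomial event count, with zero events counted as no fit, the no-fit share for smoking + PTV is 82, 57, 38, 26 and 13% at true rates of 5, 10, 15, 20 and 30%.

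**Sensitivity.** At n = 30 the shares at 2, 3, 5 and 8 events are 60, 39, 19 and 8%, so replacement of non-completers changes little. A different set-up, with two binary covariates at 50% prevalence and a 10% event rate, gives separation in 55% of trials with no effect and 72% with odds ratios of 4. A further 7% or so have no events at all.

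**Regimen.** Under section 4.1 the 5-fraction group has no recent smoker and no PTV of 10 cc or more. With regimen added, three groups must each contain an event: 5-fraction non-smokers, 16-fraction non-smokers and 16-fraction smokers. Two events cannot fill three groups, which explains the 100%.

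**The case against.** The strongest reply is that little depends on this model. The objective and the endpoint are rates, section 10.3.2.4 already commits to characterising them, and no decision rule uses the regression. That stands, and it limits the weight of the point.

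A second reply is that the section says only logistic regression. It neither requires ordinary maximum likelihood nor rules out penalised or exact fitting. That also stands: the no-fit shares describe one implementation, and a reader should not infer that the model can never be fitted. Penalisation gives a finite estimate but does not supply missing information, so the imprecision remains.

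Third, covariates, smoker share, PTV distribution and event rate are all assumed, and the no-fit share at 3 events runs from 26 to 54% across settings. Part of the phase I safety account is not in the available text and may give a better rate. The percentages are therefore indicative. The conclusion needs only that events are few.

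A reader might also infer that smoking and PTV effects can never be told apart from regimen. The documents do not support that. The rule in section 4.1 is an either/or, so the 16-fraction group can contain both smokers and non-smokers, and PTV can vary within both regimens. The confounding is strong, and separation would be poor at this size, but it is not impossible in principle.

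**Conclusion.** The concern holds as a limited point about one secondary analysis. At assumed rates of 5 to 30%, about 1 to 8 of 25 patients would have a grade 3-5 event. Under ordinary maximum likelihood with two assumed covariates, roughly 60% of data sets at 2 events and 9% at 8 have no finite fit, and the remainder give intervals too wide to identify or exclude a predictor. Confounding with regimen is conditional on smoking or PTV entering the model, which the rationale suggests but the analysis plan does not state.

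It would be wrong to infer that the safety results or the trial's main conclusion are compromised. The toxicity rates and the local-failure endpoint do not depend on this model. The sentence should be changed because it promises a determination that the data cannot deliver.

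**What to change.** Replace the regression sentence in section 10.3.2.4 with:

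> The number and proportion of treated patients with at least one related grade 3-5 event will be reported with exact 95% confidence intervals, separately for acute and late toxicity, overall and by regimen, with the number of patients still under follow-up given for late toxicity. Associations with recent smoking and PTV will be shown only as single-factor Firth-penalised (profile-likelihood interval) or exact logistic estimates; they are exploratory, strongly confounded with regimen, and no predictor will be declared.

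The follow-up count matters because a simple proportion treats patients who die or are lost early as free of late toxicity. For scale, 3/25 = 12% has an exact 95% interval of 2.5 to 31.2%, and 5/25 = 20% one of 6.8 to 40.7%.

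The change needs no new data. Its cost is the loss of adjusted odds ratios. The single-factor estimates are finite under Firth but remain very wide: 2/8 recent smokers against 1/17 others gives an odds ratio of (2.5/6.5)/(1.5/16.5) = 4.2, with a profile 95% interval of about 0.47 to 53. They could reasonably be omitted.

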10.3.2.8 Laryngectomy-free survival probability at 2 years

Kaplan-Meier statistics will be used, with death or laryngectomy serving as events.

10.3.2.9 Overall survival at 2 years

Kaplan-Meier statistics will be used.

11.0 STUDY MANAGEMENT

11.1 Conflict of Interest

Any investigator who has a conflict of interest with this study (patent ownership, royalties, or financial gain greater than the minimum allowable by their institution, etc.) must have the conflict reviewed by the UTSW COI Committee and IRB according to UTSW Policy on Conflicts of Interest. All investigators will follow the University conflict of interest policy.

11.2 Institutional Review Board (IRB) Approval and Consent

It is expected that the IRB will have the proper representation and function in accordance with federally mandated regulations. The IRB must approve the consent form and protocol.

In obtaining and documenting informed consent, the investigator should comply with the applicable regulatory requirement(s), and should adhere to Good Clinical Practice (GCP) and to ethical principles that have their origin in the Declaration of Helsinki.

Before recruitment and enrollment onto this study, the subject will be given a full explanation of the study and will be given the opportunity to review the consent form. Each consent form must include all the relevant elements currently required by the FDA Regulations and local or state regulations. Once this essential information has been provided to the subject and the investigator is assured that the subject understands the implications of participating in the study, the subject will be asked to give consent to participate in the study by signing an IRB-approved consent form.

Prior to a patient's participation in the trial, the written informed consent form should be signed and personally dated by the subject and by the person who conducted the informed consent discussion.

For patients with cognitive impairment or other limited decision making capacity, the subject and/or their LAR will be given a full explanation of the study and will be given the opportunity to review the consent form. Consent form may be signed by the patient and/or legal guardian if investigator determines that subject is willingly able to sign and complete protocol specific procedures for the duration of the study. Safeguards and/or precautions that will be taken to minimize risks/harms during the conduct of the study for individuals with cognitive impairment or other limited decision making capacity include, but is not limited to:

• Extra time to review to the ICF (e.g. phone call over the phone with the patient or LAR, then present ICF and give days to weeks for full consideration of all benefits and risks)

- Peer to peer conversation, if requested by the patient and/or LAR, between the treating research physician and the patient's primary caregiver, to discuss the protocol treatment and discuss the trial's impact to the patient's ongoing care. This will require a signed medical release waiver
- Discuss the option of having a social worker involved as needed not only for the
 patient and LAR to receive resources as needed, but also to advise the research
 team of any potential risks/harms to the patient due to the patient's impairment
 and its progression

11.3 Required Documentation (for multi-site studies)

Not applicable.

11.4 Registration/Randomization Procedures

Research staff will have online access to UTSW REDCap, and all patients will be registered electronically through REDCap. All subjects consenting to participate in any aspect of the trial must be registered on REDCap before initiating protocol activities. The eligibility checklist and confirming documentation will be entered electronically through the system.

All research data will be recorded and entered into Case Report Forms using REDCap.

Following registration, research staff from CRO will review all relevant data to ensure eligibility criteria have been met.

The first number of the subject's ID will refer to the treatment site. The ordering is:

01: UTSW

We will use this system in the future event of collaboration with other departments.

New subjects will receive a secondary number beginning with 001 upon study consent such that the first subject consented is numbered 001, the second subject consented receives the number 002, etc. Upon confirmation of eligibility and enrollment as per the afore-mentioned instructions, the subject will be assigned a tertiary number in the order of enrollment.

For example, the first patient consented and enrolled at UTSW will have the number 01-001-001.

Each newly consented subject should be numbered using the schema provided above. Upon registration, the registrar will assign the additional registration/randomization code according to the numbering schema outlined above, which should then be entered as the patient study id in Velos upon updating the status to enrolled.

The numbering schema should clearly identify the site number; the sequential number of the subject enrolled as well as the status of the subjects enrolled so that the number of subjects consented versus the number of subjects actually enrolled may be easily identified.

11.5 Data Management and Monitoring/Auditing

REDCap is the UTSW SCCC institutional choice for the electronic data capture of case report forms for this and all SCCC Investigator Initiated Trials. REDCap will be used for

electronic case report forms in accordance with Simmons Comprehensive Cancer Center requirements, as appropriate for the project.

Trial monitoring will be conducted no less than annually and refers to the review of trial related activity and documentation performed by the DOT, which includes but is not limited to accuracy of case report forms, protocol compliance, timeliness and accuracy of Velos entries and AE/SAE management and reporting. Documentation of trial monitoring will be maintained along with other protocol related documents and will be reviewed during internal audit.

Toxicity reviews will be performed at the end of study. These reviews will be documented by the study team and/or the UTSW Simmons Comprehensive Cancer Center (SCCC) Data Safety Monitoring Committee (DSMC).

The UTSW Simmons Comprehensive Cancer Center (SCCC) Data Safety Monitoring Committee (DSMC) is responsible for monitoring data quality and patient safety for all UTSW SCCC clinical trials. As part of that responsibility, the DSMC reviews all serious adverse events and UPIRSOs in real time as they are reported and reviews adverse events on a quarterly basis. The quality assurance activity for the Clinical Research Office provides for periodic auditing of clinical research documents to ensure data integrity and regulatory compliance. A copy of the DSMC plan is available upon request.

The SCCC DSMC meets quarterly and conducts annual comprehensive reviews of ongoing clinical trials, for which it serves as the DSMC of record. The Quality Assurance Coordinator (QAC) works as part of the DSMC to conduct regular audits based on the level of risk. Audit findings are reviewed at the next available DSMC meeting. In this way, frequency of DSMC monitoring is dependent upon the level of risk. Risk level is determined by the DSMC Chairman and a number of factors such as the phase of the study; the type of investigational agent, device or intervention being studied; and monitoring required to ensure the safety of study subjects based on the associated risks of the study. Protocol-specific DSMC plans must be consistent with these principles.

